4.6 Registration to Correlative and Companion Studies

4.6.1 Registration to Substudies Described in [Section 14.0](#)

There are 2 substudies within Alliance A021501. These correlative science studies must be offered to all patients enrolled on Alliance A021501 (although patients may opt to not participate). These substudies do not require separate IRB approval. These substudies included within Alliance A021501 are:

- Alliance A021501-PP1, Pharmacogenetic studies in Alliance A021501 ([Section 14.1](#))
- Alliance A021501-IM1, Imaging science studies in Alliance A021501 ([Section 14.2](#))

If a patient answers “yes” to “I agree to have my specimen collected and I agree that my specimen sample(s) and related information may be used for the laboratory study(ies) described above,” they have consented to participate in the substudies described in [Section 14.1](#). The patient should be registered to Alliance A021501-PP1 at the same time they are registered to the treatment trial (A021501). Samples should be submitted per [Section 6.2](#).

If a patient answers “yes” to “I agree have my scan images be collected and submitted for the research stated above,” they have consented to participate in the substudy described in [Section 14.2](#). The patient should be registered to Alliance A021501-IM1 at the same time they are registered to the treatment trial (A021501). Images should be submitted per [Section 6.4](#).

4.7 Stratification Factors and Treatment Assignments

Note: Arm 2 closed to new patient enrollment on 08/13/2018.

ECOG PS: 0 vs. 1

5.0 STUDY CALENDAR

Note: Arm 2 closed to new patient enrollment on 08/13/2018.

The pre-study intervals are guidelines only. Laboratory and clinical parameters during treatment are to be followed using individual institutional guidelines and the best clinical judgment of the responsible physician. It is expected that patients on this study will be cared for by physicians experienced in the treatment and supportive care of patients on this trial.

Pre-study Testing Intervals

- To be completed \leq 28 DAYS before pre-registration: CT/MRI scans used for staging
- To be completed \leq 21 DAYS before registration: All laboratory studies, history and physical

	Prior to Pre-Reg	Prior to Reg*	Day 1 of each cycle of mFOLFIR-INOX*	RT (day 1 to day 5) (Arm 2 only)**	Surgery	Day 1 of each cycle of FOLFOX *	Post Tx Follow-up***
Tests & Observations							
History and Physical, Weight, PS ****		X (1)	X (1)	X (1)		X (1)	X (1)
Pulse, BP		X (1)	X (1)	X (1)		X (1)	X (1)
Height		X (1)					
Adverse Event Assessment (CTCAE) †		X (1)	X (1)	X (1)	D (1)	X (1)	
Adverse Event Assessment (PRO-CTCAE) ††		X (2)	X	X	D	X	
Registration QOL/Mental Well-being/Physical Well-being/Fatigue		X (2)					
Laboratory Studies							
CBC, Differential, Platelets		X	X	X	X	X	X (3)
Chemistry (Serum Creatinine, Electrolytes, AST, ALT, Alk. Phos., Albumin, Total Bilirubin)		X	X	X	X	X	X (3)
Pregnancy Test #		X					
CA 19-9		A	A	A	A	A	X
RT Planning							
EUS with Fiducial Placement for RT				B			
Staging							
Staging CT Scan of Chest or Chest X-ray/CT or MRI of Abdomen	X (4)		C (4)	C (4)	C (4)	C (4)	X (4)
Central Radiographic Review		C			C		
Central Pathology Review							
					X (5)		
Optional Correlative Studies: For patients who consent to participate							
Blood Specimen Sample (A021501-PP1)	Between registration and C1D1. See Section 6.2 .						
Imaging (A021501-IM1)	See Section 6.4.2 for CT images submission time points and requirements.						

* Labs completed prior to registration may be used for day 1 of cycle 1 if obtained \leq 7 days prior to treatment (except pregnancy test and CA 19-9, as detailed below). For subsequent cycles, labs, tests and observations may be obtained +/- 3 days from scheduled day of assessment. Radiographic windows are +/- 7 days from scheduled day of assessment.

** To be completed once at any point during Day 1 – Day 5 of RT for Arm 2 patients (except for PRO-CTCAE; see footnote ††). RT should begin \geq 5 days after the last dose of chemotherapy.

- *** After off-treatment (evaluation of the last treatment cycle), patients will have physical examinations, labs, and staging scans every 16 weeks (+/- 28 days) until they have reached 24 months post-registration or until documented progression, whichever occurs first. Thereafter, survival information is required every 6 months for 5 years post-registration. For patients who discontinue treatment for progressive disease or are removed from protocol treatment, survival information is required every 6 months for 5 years post-registration. See [Section 12.0](#) for removal of patients from protocol therapy.
- **** Drug dosages need not be changed unless the calculated dose changes by $\geq 10\%$.
- 1 May be performed by physician, NP, or PA responsible for oncologic care of the patient.
 - 2 To be completed after pre-registration but ≤ 21 days prior to treatment. See [Appendix I](#).
 - 3 CBC, Differential, Platelets, and Chemistry during the post-treatment follow-up period should be performed if clinically indicated. Examples of clinical indications would be fatigue, nausea, etc.
 - 4 Chest scans must be CT or chest X-ray. Abdominal baseline and restaging scans can include either a CT or MRI, although CT is preferred. Contrast should be used unless there is a medical contraindication. The same method of scanning used at baseline must be used for all subsequent evaluations. The CT must be acquired with 3 mm or less slice thickness. See [Section 7.4.1](#) for further details. Supporting documentation is to be submitted, per [Section 6.1.1](#). The baseline scan and restaging scan after completion of preoperative therapy/prior to surgery are to be centrally reviewed by the Alliance ICL at IROC Ohio, per [Section 7.4.2](#).
 - 5 Central pathology review is retrospective. Sites must submit slides within 60 days of surgery of patient. See [Section 6.2](#).
- † Solicited AEs are to be collected starting at baseline. Routine AEs are to be collected starting after registration. See [Section 9.1](#) for the list of solicited AEs. See [Section 9.4](#) for expedited reporting of SAEs. See [Section 9.2](#) for reporting of surgical AEs, to be completed within 90 days after surgery.
- †† Patients complete PRO-CTCAE by paper booklet ordered through the CTSU website. See [Section 9.1](#) for administration instructions. See [Appendix I](#) for PRO-CTCAE assessments for IRB submission and review only. See [Section 4.4](#) for ordering instructions. PRO-CTCAE booklets should be administered at the following time points: ≤ 21 days prior to treatment; day 1 of each cycle of mFOLFIRINOX (+/- 3 days); RT days 1-5 (Arm 2 only); prior to surgery (+/- 7 days); and day 1 of each cycle of FOLFOX (+/- 3 days).
- # For women of childbearing potential (see [Section 3.3.6](#)). Must be done ≤ 7 days prior to registration.
- A CA19-9 may be performed < 28 days prior to registration. Subsequently, CA19-9 may be performed +/- 14 days from the scheduled date. During treatment, CA19-9 should be performed every 28 days. For patients who have normal CA19-9 levels at baseline, continued testing of CA19-9 is not required.
- B EUS/fiducial marker placement must be attempted for patients in the RT arm. Immediately following review of first restaging studies, planning for EUS/fiducial placement and RT simulation should be scheduled to be performed during either cycle 5 or 6 of mFOLFIRINOX.
- C Restaging scans should be performed for both Arm 1 and Arm 2 at the following time points: 1) after the first 4 cycles of mFOLFIRINOX; 2) prior to surgery; 3) post-surgery but prior to first cycle of FOLFOX; 4) after 4 cycles while on FOLFOX. The baseline and restaging scan after completion of preoperative therapy and prior to surgery are to be centrally reviewed by the Alliance ICL at IROC Ohio per [Section 7.4.2](#). After protocol treatment, scans should be performed per the schedule indicated by footnote “****”.
- D Surgery-related AEs should be assessed and captured within 90 days of surgery.

6.0 DATA AND SPECIMEN SUBMISSION

6.1 Data Collection and Submission

Data collection for this study will be done exclusively through the Medidata Rave clinical data management system. Access to the trial in Rave is granted through the iMedidata application to all persons with the appropriate roles assigned in Regulatory Support System (RSS). To access Rave via iMedidata, the site user must have an active CTEP-IAM account (check at <https://ctepcore.nci.nih.gov/iam>) and the appropriate Rave role (Rave CRA, Read-Only, CRA Lab Admin, SLA, or Site Investigator) on either the LPO or participating organization roster at the enrolling site. To hold Rave CRA role or CRA Lab Admin role, the user must hold a minimum of an AP registration type. To hold the Rave Site Investigator role, the individual must be registered as an NPIVR or IVR. Associates can hold read-only roles in Rave.

Upon initial site registration approval for the study in RSS, all persons with Rave roles assigned on the appropriate roster will be sent a study invitation e-mail from iMedidata. To accept the invitation, site users must log into the Select Login (<https://login.imedidata.com/selectlogin>) using their CTEP-IAM user name and password, and click on the “accept” link in the upper right-corner of the iMedidata page. Please note, site users will not be able to access the study in Rave until all required Medidata and study specific trainings are completed. Trainings will be in the form of electronic learnings (eLearnings), and can be accessed by clicking on the link in the upper right pane of the iMedidata screen.

Users who have not previously activated their iMedidata/Rave account at the time of initial site registration approval for the study in RSS will also receive a separate invitation from iMedidata to activate their account. Account activation instructions are located on the CTSU website, Rave tab under the Rave resource materials (Medidata Account Activation and Study Invitation Acceptance). Additional information on iMedidata/Rave is available on the CTSU members’ website under the Rave tab at www.ctsu.org/RAVE/ or by contacting the CTSU Help Desk at [REDACTED]

A Schedule of Forms is available on the Alliance study webpage, within the Case Report Forms section. The Schedule of Forms is also available on the CTSU site within the study-specific Education and Promotion folder, and is named Time & Events.

6.1.1 Supporting Documentation

This study requires supporting documentation for diagnosis, response, and progression. Supporting documentation will include radiology, pathology, and surgical operation reports; these must be submitted at the following time points:

- **Baseline:** Imaging report, pathology/cytology report, clinic note
- **Completion of preoperative therapy:** Imaging report
- **Resection:** Operative report, pathology report
- **Response:** Imaging report
- **Progression/relapse/recurrence:** Imaging report, and pathology report if applicable

6.2 Specimen Collection and Submission

For all patients registered to Alliance A021501: Retrospective histopathology review will be conducted using a representative paraffin embedded block of pancreatic tumor from the surgical resection specimens. If the surgical resection specimen does not show residual cancer, the specimen from the diagnostic biopsy or a representative FNA cytologic slide should be submitted in addition to the surgical specimen. **The submission of tumor (or diagnostic pathology specimen for patients that have a pCR at surgery) for histopathology review is**

required for all patients registered to this study, including those who are found to be ineligible and those who do not receive protocol therapy.

For patients registered to substudy A021501-PP1: All participating institutions must ask patients for their consent to participate in the correlative substudies planned for Alliance A021501-PP1, although patient participation is optional. Biomarker and pharmacogenetic studies will be performed. Rationale and methods for the scientific components of this study is described in [Section 14.1](#).

For patients who consent to participate, specimens will be collected at the time points listed in the table below:

	Prior to Initiation of Treatment	At surgery	Storage/ Shipping	Submit to:
Mandatory for all patients on A021501:				
Paraffin block AND one stained H&E slide	A	X	Ambient temp/ ship overnight	WUSTL
To be submitted ONLY for patients that consent to A021501-PP1*:				
Whole blood¹ (EDTA/lavender top)	1 x 10 mL		Cool pack/ship overnight	WUSTL
To be submitted ONLY for patients that consent to biobanking for future research**:				
Paraffin block	A		Ambient temp/ ship overnight	WUSTL

- * Patients who consent to A021501-PP1 are those who answer “Yes” to the model consent question, “I agree to have my blood specimen collected and I agree that my specimen samples and related information may be used for the laboratory studies described above.”
- ** Patients who consent to biobanking for future research are those who answer “Yes” to the model consent question, “My samples and related information may be kept in a Biobank for use in future health research.”
- A To be collected any time prior to the initiation of treatment. For patients who have a pCR at time of surgery, if possible, please submit at least one H&E slide from pretreatment FNA or core biopsy. If possible, please also submit a paraffin-embedded tissue block or block-alternative (as many unstained slides as possible, up to 10) from the pretreatment FNA or core biopsy. For patients who consent to biobanking for future research and who do not have a pCR at time of surgery, if possible, please also submit a paraffin-embedded tissue block or block-alternative (as many unstained slides as possible, up to 10) from pretreatment FNA or core biopsy. For patients who consent to biobanking for future research and who do have a pCR at time of surgery, no additional submissions are required if a pretreatment specimen was already submitted for mandatory histopathology review. See [Section 6.2.2](#) for details.
- 1 For patients who consent to correlative study A021501-PP1, whole blood is to be used for pharmacogenomic analyses described in [Section 14.1](#). This tube of blood is preferred to be collected prior to the initiation of treatment but can be collected at any time while a consented patient is on study.

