6.2.3 Blood Specimen Submission for A021501-PP1

For patients who consent to participate, whole blood specimen will be used for the pharmacogenomic studies described in [Section 14.1](#). This specimen should be collected prior to the initiation of protocol treatment.

Collect 10 mL of peripheral venous blood in an EDTA (lavender) tube. The tubes should be inverted several times to mix the EDTA and refrigerated until shipped on cool pack by overnight mail to the Alliance Biorepository at Washington University (WUSTL). The specimens should be shipped the same day that the blood is drawn in ambient temperature per [Section 6.2.1](#).

Label specimens with the following identification information:

1. Procurement Date and Time
2. Patient Initials
3. Alliance Patient ID Number
4. Alliance Study Number (i.e. A021501-PP1)
5. Sample Type (i.e. Whole Blood)

Ship blood per instructions in [Section 6.2.1](#).

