14.1.2 Objectives

Primary Objective

To test the effect of the rs2853564 *VDR* variant on the 18 months OS rate using both arms combined. We hypothesize that patients with the GG genotype have worse survival than patients with either the AA or AG genotype.

Secondary Objectives

1. To test an interaction between the rs2853564 *VDR* variant and treatment arm on the 18 months OS rate. We hypothesize that the effect of the rs2853564 *VDR* variant on survival might differ between the two arms.

Statistical Methods: Logistic regression will be used to test this interaction. The response variable will be an indicator for survival at 18 months. The predictor variables will include clinical variables, an indicator for rs2853564 *VDR* variant [GG vs. (AA or AG)] and an indicator for treatment arm, and the interaction between variant and treatment arm.

2. To discover novel candidate genes associated with the 18 months OS rate and severe toxicity of chemotherapy. We hypothesize that the genotyping a large series of common germline variants through a genome wide approach will allow the identification of novel gene markers of survival and severe toxicity.
3. To run association analyses with the many molecular markers identified in the correlative science section of this protocol. We hypothesize that the information on the germline variation of patients will associate with molecular markers that relate to constitutional systems like inflammation, immunity, angiogenesis, stromal functions, and others.

Statistical Methods: Penalized regression methods such as LASSO or elastic net will be utilized to determine combinations of genes that may predict the outcomes. Clinical covariates will be forced into the models. Cross validation will be used in the model building to reduce over-fitting. The logistic framework will be used for dichotomous variables, and a Gaussian or time-to-event framework for continuous or survival outcomes, respectively. We will stay abreast of the literature for modeling strategies that are appropriate for such modeling.

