14.1.3 Methods

The germline DNA of patients who have consented to these analyses will be collected from peripheral blood as described in [Section 6.2](#).

Genotyping of the rs2853564 *VDR* variant will be conducted by TaqMan assay (Applied Biosystems, Foster City, CA) per the manufacturer's instructions using a CFX384 Real-Time System (Bio-Rad, Hercules, CA) and performed in the laboratory of [name] at the University of North Carolina at Chapel Hill. Sanger-based DNA sequencing (Mammalian Genotyping Core at the University of North Carolina at Chapel Hill) will be used to validate representative samples and determine thresholds for allelic discrimination. The allele frequency will be compared with those previously reported from the HapMap and 1,000 Genomes

projects. Deviation from Hardy-Weinberg equilibrium ($p < 0.01$ for significance) will be tested to evaluate genotyping accuracy.

Genome-wide genotyping will be performed by the OmniExpress Exome chip, which enables whole-genome genotyping of over 700,000 single nucleotide polymorphism (SNP) loci. This platform gives an outstanding breadth of coverage over the genome for the planned association studies. It will be performed at the Mammalian Genotyping Core at the University of North Carolina at Chapel Hill.

Exome and whole sequencing could be also performed from germline and somatic DNA to detect associations between outcome and rare variants.

Logistic regression will be used to assess the relationship between rs2853564 VDR variant and 18 month OS rate. The treatment assignment and the interaction term between rs2853564 VDR variant and treatment assignment will be entered in the model in order to examine whether the effect of the rs2853564 VDR variant differs between 2 arms.

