Fisher's Exact test will be used to assess the association of the GG genotype with worse 18 month OS. With a total sample size of $N=125$ in both arms, and 85% expected rate of consent to this study, we expect a sample size of 106 for this aim. We assume 63% 18 month OS rate (the alternative hypothesis in the primary aim of this trial) and 16% prevalence of the GG variant. We expect $n=17$ GG variant patients. Under these assumptions, a Fisher's Exact test has 82% power to detect a difference of 44% versus 82% (i.e. a delta of 38%) 18 month OS rates between the groups defined by the GG variant. Nonparametric methods such as recursive partitioning for classification, regression and survival trees (RPART) will be used to explore a possible predictive value of the GG genotype (secondary objective 1), and prognostic value of common variants (secondary objective 2) [44]. In secondary objective 4, generalized linear model methods and penalized regression together with cross validation will be used to evaluate the association between germline variation and molecular markers of inflammation, immunity, angiogenesis, and stromal functions in an exploratory fashion.

Similar approaches to *Quality Control and Normalization of Expression Data, Differential expression, Model Building, and Internal Model Validation* will be employed. We will stay abreast of the literature for methods that are appropriate for data analysis. A detailed analysis plan will be formulated prior to actual data analysis.

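### Section 6.2 footnote 1 allows the PP1 blood to be drawn at any time on study, although three other places put it before treatment; any late draws would make the VDR test against 18-month survival depend on living to the draw.

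*Combined protocol and SAP*

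**What the plan says.** The plan times the PP1 whole-blood sample in four places.

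- Section 5.0, study calendar: "Between registration and C1D1".
- Section 6.2, specimen table: the tube is listed in the column for samples taken before treatment starts.
- Section 6.2.3: "This specimen should be collected prior to the initiation of protocol treatment".
- Section 6.2, footnote 1 to the specimen table: a pre-treatment draw is preferred, but the blood "can be collected at any time while a consented patient is on study". The documents do not define when a patient stops being on study.

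Section 4.6.1 fixes entry to the substudy: "The patient should be registered to Alliance A021501-PP1 at the same time they are registered to the treatment trial". A patient can therefore be in PP1 before any blood has been drawn.

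Section 14.1.3 takes its collection rule from the section that holds the footnote: "The germline DNA of patients who have consented to these analyses will be collected from peripheral blood as described in" Section 6.2. The primary objective in Section 14.1.2 concerns the effect of the "variant on the 18 months OS rate using both arms combined". Section 14.1.3 says Fisher's exact test "will be used to assess the association of the GG genotype with worse 18 month OS", and adds logistic regression. Section 13.1.1 counts 18-month survival from randomization.

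The sample size in Section 14.1.3 starts "With a total sample size of $N=125$ in both arms, and 85% expected rate of consent to this study" and arrives at 106 patients, of whom 17 are GG. It makes no allowance for consenters without a sample. Section 14.1 has no landmark, no delayed entry, no restriction to pre-treatment samples and no rule for missing genotypes. It promises a detailed analysis plan before the data are analysed.

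**The concern.** A site that draws the PP1 tube at surgery or during FOLFOX follows footnote 1, which sits in the section that the PP1 methods cite. A tube drawn in month 5 exists only if the patient lived to month 5, yet the endpoint runs from randomization. A consenter who dies before a deferred draw has no genotype and leaves the analysis, and is by definition an 18-month failure. The missing data therefore depend on the outcome. This is left truncation without an adjustment for it.

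If GG patients do worse, as PP1 hypothesises, GG loses proportionately more patients. Observed survival then rises in both groups and rises more in GG, so the difference narrows. The GG group is planned at only 17, so the test has little room for such losses. A later analysis plan can adjust for late entry, but it cannot recover a genotype that was never collected.

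**Working it through.** **Inputs from Section 14.1.3.** 125 × 0.85 = 106 consenters; 106 × 0.16 = 17 GG, leaving 89 AA/AG; 18-month survival of 44% against 82%; stated power 82%. The level and sidedness of the test are not given.

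**The stated power.** Enumerating both binomials (17 and 89) gives exact Fisher power of 82.9% with 0.025 in one tail, which matches the stated 82%. The two-sided 5% test that orders tables by probability gives 86.1%. Both are shown below. The pair 44% and 82% averages (17 × 0.44 + 89 × 0.82)/106 = 75.9%, not the 63% that the section also assumes. I keep the pair because it reproduces the stated power.

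**Assumptions that the documents do not supply.** Survival is exponential within genotype, so S(t) = p^(t/18). A share L of consenters, unrelated to prognosis, is drawn at month t if alive, and the rest at baseline. I take t = 5 and t = 9 from the schedule, without dose delays:

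- Day 1 of cycle 8 falls 14 weeks after C1D1, and surgery follows 4 to 8 weeks later. With up to 2 weeks from registration to treatment, surgery falls at about 18 to 24 weeks.
- FOLFOX starts 4 to 12 weeks after surgery and runs for 8 weeks, so it ends at about 30 to 44 weeks.

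**Formulas.** Fraction genotyped r = (1 − L) + L·S(t). Expected number genotyped = n·r. Observed 18-month survival = p/r, because every patient lost is a failure.

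**Example, L = 30%, t = 5.**

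- GG: S = 0.44^(5/18) = 0.796; r = 0.7 + 0.3 × 0.796 = 0.939; n = 17 × 0.939 = 16.0; observed 0.44/0.939 = 46.9%.
- AA/AG: S = 0.82^(5/18) = 0.946; r = 0.984; n = 89 × 0.984 = 87.6; observed 0.82/0.984 = 83.3%.
- The gap is 36.5 points instead of 38.

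| Late share | Draw month | GG / AA-AG genotyped | Observed survival, % | Gap, points | Odds ratio | Power, two-sided 5% | Power, one tail 0.025 |
|---|---|---|---|---|---|---|---|
| none | – | 17 / 89 | 44.0 / 82.0 | 38.0 | 0.172 | 86% | 83% |
| 10% | 5 | 16.7 / 88.5 | 44.9 / 82.4 | 37.5 | 0.174 | 86% | 82% |
| 10% | 9 | 16.4 / 88.2 | 45.5 / 82.8 | 37.2 | 0.174 | 83% | 79% |
| 30% | 5 | 16.0 / 87.6 | 46.9 / 83.3 | 36.5 | 0.176 | 82% | 78% |
| 30% | 9 | 15.3 / 86.5 | 48.9 / 84.4 | 35.4 | 0.177 | 80% | 73% |
| 50% | 5 | 15.3 / 86.6 | 49.0 / 84.3 | 35.3 | 0.179 | 79% | 74% |
| 50% | 9 | 14.1 / 84.8 | 52.9 / 86.1 | 33.2 | 0.182 | 75% | 65% |
| 100% | 5 | 13.5 / 84.2 | 55.3 / 86.6 | 31.4 | 0.190 | 73% | 62% |
| 100% | 9 | 11.3 / 80.6 | 66.3 / 90.6 | 24.2 | 0.206 | 51% | 41% |

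Power uses group sizes rounded to whole patients, so differences of a point or two partly reflect rounding. The 100% rows are an extreme bound.

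**Pooled survival.** A true 63%, by 0.63/[(1 − L) + L·0.63^(t/18)], would appear as 64% at L = 10% and as 65% (month 5) or 67% (month 9) at L = 30%.

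**If genotype has no effect.** Both groups lose the same fraction and keep equal rates, so Fisher's test stays valid. At 63% survival its exact two-sided size is 3.3% with no late draws and 3.9%, 3.3% and 2.6% with 25% late at month 6, 50% at month 10 and 100% at month 10.

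**Cost of discarding late samples.** Dropping them leaves 15 / 80, 12 / 62 or 8 / 44 patients at 10%, 30% or 50% late. Two-sided power is then 82%, 71% or 54%, below the power with late samples kept in every case at those shares.

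**The case against.** The main points on the other side are these.

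- **Pre-treatment is the default.** The calendar, the table column and Section 6.2.3 all require it, and footnote 1 prefers it. A reader might infer that the VDR test does run partly on survivors. The documents do not support that: they give no share of late draws, and if none are late the effect is nil. This stands, and the point is conditional for that reason.
- **A late tube measures genotype correctly.** Germline genotype does not change, and no survival time is credited to the wrong genotype. This is true, but the problem is who is missing, not what is measured.
- **False positives.** A reader might infer that late draws could create a spurious association. The calculation shows the opposite direction: no inflation of type I error, a smaller gap, and an odds ratio that barely moves (0.172 to 0.176 at 30% late, month 5).
- **The footnote may rescue patients.** Deleting it does not make a missed baseline draw happen; a late tube may be the only genotype that such a patient provides. This stands, and so does the finding that excluding late samples costs more power than keeping them. It argues against discarding samples, not against one clear collection rule.
- **Severe toxicity.** A reader might extend the concern to the severe-toxicity analysis. A patient with early severe toxicity who is alive and on study can still be drawn under footnote 1, and nothing in the documents shows selective loss. I do not make that claim.
- **Later handling.** Section 6.2.1 requires the collection date on every specimen and Section 6.2.3 the procurement date and time, so late samples can be identified. That makes adjustment feasible, but Section 14.1 does not yet specify it.

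**Conclusion.** The timing texts conflict, and the PP1 analysis has no rule for samples drawn late. Any late draws would overstate survival among genotyped patients and pull the GG comparison toward the null. At 10% late the gap falls from 38 to about 37 points, and two-sided power is 83-86% against 86%. At 30% late the gap is about 35 to 36.5 points and two-sided power 80-82%; under the one-tail rule that matches the protocol's 82%, power falls from 83% to 73-78%.

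These figures rest on exponential survival, the 44% and 82% pair, draws at month 5 or 9, and an assumed late share. The conflict in wording is certain; the size of the bias is not known. The point concerns an optional substudy and does not touch the trial's primary endpoint.

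**What to change.** 1. Reword footnote 1 in Section 6.2 to agree with 5.0 and 6.2.3: PP1 blood is drawn between registration and C1D1.
2. Keep any late samples. In Section 14.1.3, add a time-to-event model for genotype and OS, with time from randomization and delayed entry at the recorded procurement date. State its assumption that, among patients still alive, the timing of the draw is unrelated to prognosis.
3. Report the 18-month Fisher and logistic tests with all samples and, as a sensitivity analysis, with pre-treatment samples only.
4. Report how many consenters died or left the study before a draw.

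The cost is one footnote, a few sentences of analysis text and a little extra analysis. The procurement date is already collected. The pre-treatment-only test has less power (71% two-sided at 30% late), which is why it is a sensitivity analysis and not a replacement.
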